5.9.6 Vital Signs

Systolic blood pressure, diastolic blood pressure, pulse, body temperature, respiratory rate, weight, height and BMI will be collected. Weight (kg) will be measured at each visit and height (cm) will be measured only at the screening visit.

5.9.7 12-Lead Electrocardiogram (ECG)

Heart rate, PR interval, QTcF, RR interval, ST segment, T-wave, Heart rate, and whether the result is normal/abnormal and clinically significant/not-significant will be collected. For Day 1 of Cycle 1 and 2, 12-lead ECG will be collected before the IP administration and approximately 4 hours after IP administration which corresponds to the time when the PK C_{max} blood is drawn.

5.9.8 Laboratory Data

- Hematology (complete blood count, CBC: white blood cell (WBC) with 5-part differential (neutrophils, lymphocytes, monocytes, eosinophils, and basophils), platelet count, absolute neutrophil count (ANC), red blood cell count (RBC), hemoglobin (Hb), hematocrit (Hct))
- Blood chemistry: sodium, potassium, chloride, carbon dioxide or bicarbonate (if required), blood urea nitrogen (BUN), creatinine, glucose (fasting), total protein, albumin, calcium, amylase, lipase, phosphorous, magnesium, creatinine kinase (CK), uric acid, total bilirubin, AST, ALT, and ALP
- Serological tests: HIV antibody (if HIV antibody result is positive, HIV-1 antibody and HIV-2 antibody should be conducted), HBs antigen, HBs antibody, HBC antibody, HCV antibody
- Coagulation tests: prothrombin time expressed as either prothrombin time (PT) or international normalized ratio (INR) and partial thromboplastin time (PTT or aPTT)
- Urinalysis: specific gravity, protein, glucose, occult blood, and microscopic examination if indicated
- Pregnancy test: it will be carried out only for female subjects with child-bearing potential (serum or urine).

5.9.9 Physical Examination

Any abnormal physical findings on eye, ears, nose, throat, neck, thyroid, cardiovascular system, respiratory system, gastrointestinal system or mouth, dermatologic system, extremities, musculoskeletal system,

central and peripheral nervous system, lymph nodes will be collected. Whether the finding is clinically significant will also be checked.

5.9.10 ECOG performance

ECOG performance score (0,1,2,3,4) will be collected.

Table 7. ECOG Grade

ECOG Grade	Description
0	Fully active, able to carry on all pre-disease activities without restriction.
1	Restricted in physically strenuous activity but ambulatory and able to carry out work of a light or sedentary nature (light house work, office work).
2	Ambulatory and capable of all self-care but unable to carry out any work activities. Up and about more than 50% of waking hours.
3	Capable of only limited self-care, confined to bed or chair more than 50% of waking hours.
4	Completely disabled. Cannot carry on any self-care. Totally confined to bed or chair.

6. DISPOSITION AND PROTOCOL DEVIATIONS

6.1 Subject Disposition

Subjects in each analysis set (ITT Set, FAS, PPS and Safety Set) will be summarized with counts and *percent* by treatment group for all enrolled subjects. Reason excluded from each analysis set will be summarized with counts by treatment group. Subjects excluded from each analysis set will be listed.

The disposition of all screened subjects will be summarized by treatment group. The number of subjects who are randomized (treated/Non-treated) and the number of subjects who are completed/Withdrawn will be summarized by treatment group. The withdrawn subject will be listed.

In addition, for subjects who prematurely discontinue from the study, the reasons for withdrawn will be summarized with counts by treatment group and for the ITT set. The number of randomized subject will also be summarized by region, country and by investigator. The number of randomized subject will be summarized with counts and percent by the stratification.

The disposition tables will include the following summaries by treatment and overall:

- Analysis populations (all subjects)
 - Enrollment by region, country and site (ITT population)
 - Summary of randomization stratification per IWRS (ITT population)
 - Study Treatment Disposition and Discontinuation (ITT population)
 - Study Status, Duration of Treatment and Study Exit (ITT population).
- Duration of Treatment (month) = (Date of last treatment admin.– Date of first treatment admin. +1)

x 12/365.25

- Duration of Study (month)
 - = Date of (End of study – Date of Randomization +1) x 12/365.25; for study discontinued/completed.
 - = Date of (the last visit – Date of Randomization +1) x 12/365.25; for study ongoing.

Data will be summarized in the following tables:

- *Table. Subject Disposition – All Screened Subjects*
- *Table. Subject Population – All Enrolled Subjects*
- *Table. Enrollment by Geographic Region – ITT*
- *Table. Enrollment by Country – ITT*
- *Table. Enrollment by Site – ITT*
- *Table. Summary of Randomization Stratification – ITT*
- *Table. Duration of Treatment – ITT*

- *List. Analysis Set – ITT*
- *List. Withdrawn Subjects – ITT*

6.2 Protocol Deviations

The study team will conduct reviews of the protocol deviation and violation (PDV) data and resulting set of PPS population subjects throughout the study, adjusting the PDV criteria as seems appropriate. The PPS population subjects set will be finalized at the blind meeting (or earlier), prior to database lock.

All protocol deviations and violations data will be listed.

Data will be summarized in the following table and list.

- *Table. Major Protocol Deviation – ITT Set*
- *List. Subjects with Major Protocol Deviation – ITT Set*

7. EFFICACY EVALUATION

7.1 Demographics and baseline characteristics

Demographics and baseline characteristics will be summarized by descriptive statistics by treatment group for the ITT set. The number of subjects, mean, standard deviation, minimum and maximum will be presented for continuous data, and the number and percentage (%) of subjects will be presented for categorical data.

For the demographics, the following variables will be summarized:

- Continuous Variables: Age (years), Weight (Kg) at baseline, Height(cm), BMI(Kg/m²) at baseline
- Categorical Variables: Sex(Male, Female), History of drug abuse (Yes, No), History of alcohol

abuse(Yes, No), Ethnicity (Hispanic or Latino, Not Hispanic or Latino), Race(American Indian or Alaska Native, Asian, Black or African American, Native Hawaiian or Other Pacific Islander, White, Others), Geographic Region (Asia pacific, North America/Europe), Disease Measurability (Measurable, Nonmeasurable), Prior Ramucirumab Treatment (Yes, No), Treatment Therapy Line (3rd, ≥ 4th)

- Age(years) = Year of consent – year of birth; If consent date is after birth date
Year of consent – year of birth-1; If consent date is before birth date
- BMI(kg/m²) = Weight(kg)/[height (cm)/100]²

Data will be summarized in the following tables.

-Table. Demographic and baseline characteristics – ITT

- List. Demographic data – ITT

7.2 Cancer History and Cancer Therapy/Surgeries/Procedures/Radiotherapy

Gastric cancer history, current cancer status, anti-cancer therapy, surgeries, procedures and radiotherapy will be summarized presenting descriptive statistics by treatment group for the ITT set. For anti-cancer therapy will be coded using WHO-DDE 2017(ATC code). The number and percentage (%) of subjects will be presented based on 'Anatomical main group(level 1)' and 'Therapeutic subgroup(level 2)' by treatment group. For surgeries/procedures, the number and percentage (%) of subjects will be presented based on Preferred Term(PT) and System Organ Class(SOC) using Medical Dictionary of Regulatory Activities (MedDRA) version 19.0 or higher. For anti-cancer therapy, surgeries/procedures and radiotherapy, p-value that tests homogeneity of proportions between treatment groups (chi-square test or Fisher's exact test) will be presented.

Data will be summarized in the following tables.

-Table. Gastric Cancer History – ITT

-Table. Current Cancer Status – ITT

-Table. Prior Anti Cancer – ITT

-Table. Prior Anti Cancer Therapy by Anatomical and Therapeutic Class – ITT

-Table. Post Anti Cancer Therapy by Anatomical and Therapeutic Class – ITT

-Table. Prior Surgeries and Procedures by SOC and PT – ITT

-Table. Concomitant Surgeries and Procedures by SOC and PT – ITT

-Table. Post Surgeries and Procedures by SOC and PT – ITT

-Table. Prior Radiotherapy – ITT

-Table. Concomitant Radiotherapy – ITT

-Table. Post Radiotherapy – ITT

7.3 Medical History

Medical History will be summarized by treatment group for the ITT set. The number and percentage (%) of subjects will be presented based on Preferred Term (PT) and System Organ Class(SOC) using Medical

Dictionary of Regulatory Activities (MedDRA) version 19.0 or higher. P-value that tests homogeneity of proportions between treatment groups (chi-square test or Fisher's exact test) will be presented.

Data will be summarized in the following tables.

- *Table. Medical History by SOC and PT – ITT*

7.4 Prior and Concomitant Medications

All collected medications will be classified as Prior or Concomitant Medications according to Section 5.5, and coded by using WHO-DDE 2017(ATC code). For ITT set, the number and percentage (%) of subjects will be presented based on 'Anatomical main group (level 1)' and 'Therapeutic subgroup(level 2)' by treatment group. P-value that tests homogeneity of proportions between treatment groups (chi-square test or Fisher's exact test) will be presented

Data will be summarized in the following tables.

- *Table. Prior Medication by Anatomical and Therapeutic Class – ITT*

- *Table. Concomitant Medication by Anatomical and Therapeutic Class – ITT*

- *Table. Post Medication by Anatomical and Therapeutic Class – ITT*

7.5 Efficacy Analysis

7.5.1 Multiple Comparison Procedure on Primary and Key Secondary Endpoints

To control the family-wise error rate (FWER) on testing multiple hypotheses of interest, the fixed sequence closed testing procedure will be used. In this fixed sequence procedure, each hypothesis will be sequentially tested with two-sided 5% level only if higher level hypothesis is rejected. For this fixed sequential testing, the primary and key secondary efficacy endpoints will be tested using the ITT set. Specifically,

1. Test OS with two-sided 5% level
2. If OS is significant, test PFS (based on central review) with two-sided 5% level
3. If OS and PFS are significant, test ORR (based on central review) with two-sided 5% level

If a prior test is not statistically significant, then the subsequent analyses will be exploratory rather than confirmatory.

7.5.2 Primary Efficacy Analysis

- Overall Survival (OS): Time from randomization to death. Subjects alive or lost to follow-up are censored at the date the subject was last known to be alive.

The primary efficacy endpoint (OS) will be analyzed using ITT, FAS and PPS. The primary efficacy analysis will be conducted using the ITT set. The final analysis will be conducted when approximately 325 events are observed.

The comparison of OS between the two treatment groups will be performed with a logrank test stratified on the randomization stratification variables Geographic region (Asia vs. North America/Europe), Prior

ramucirumab treatment (Yes vs. No), and Treatment therapy line (3rd vs. ≥ 4th) at the two-sided alpha=0.05 level of significance.

In order to estimate the hazard ratio, a Cox proportional hazards regression model will be fitted with treatment group as a factor and the randomization stratification variables [Geographic region (Asia vs. North America/Europe), Disease measurability (measurable vs. nonmeasurable), Prior ramucirumab treatment (Yes vs. No), and Treatment therapy line (3rd vs. ≥ 4th)] as covariates. The hazard ratio and its 95% confidence interval will be presented.

Kaplan-Meier estimates will be calculated for each treatment group to construct the survival curve. The median overall survival and its 95% CI (based on Greenwood formula) will be presented. The primary endpoints will also be analyzed using the FAS and PPS.

Data will be summarized in the following tables and figures.

-Table. Overall Survival – ITT

-Table. Overall Survival – FAS

-Table. Overall Survival – PPS

-Figure. Kaplan Meier Plot for Overall Survival – ITT

-Figure. Kaplan Meier Plot for Overall Survival – FAS

-Figure. Kaplan Meier Plot for Overall Survival – PPS

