### **3) Phase III clinical study in patients with advanced or metastatic gastric cancer**

A multicenter, randomized, double-blind, phase III study was conducted in patients who failed to second-line therapy. The study was designed as 28 days/cycle, consisting of YN968D1 850 mg (as apatinib mesylate) group and Placebo group. The primary efficacy endpoint was overall survival. Randomization was done centrally and was stratified by the number of metastatic sites ( $\leq 2$  or  $> 2$ ). A total of 267 randomly assigned subjects were included in FAS population; 176 in the YN968D1 group and 91 in the Placebo group. As for the efficacy, mean overall survival was statistically greater for the YN968D1 group than for the Placebo group (6.5 months versus 4.7 months; HR= 0.709; 95% CI (0.537~0.937);  $p < 0.0149$ ). mPFS also showed the same result (2.6 months versus 1.8 months; HR= 0.444, 95%CI (0.331~0.595),  $P < 0.001$ ). ORR was 2.84% and 0.00% for the YN968D1 group and the Placebo group, respectively. As for the safety, YN968D1 was mostly controlled by treatment discontinuation or reduction. The most common adverse events were hand-foot skin reaction (HFSR), proteinuria and hypertension. In conclusion, the efficacy and safety of YN968D1 850 mg were confirmed in advanced and metastatic gastric cancer.

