#### 8.3.4. Primary Efficacy Analysis

The primary efficacy analysis will be conducted using the ITT set.

Overall Survival (OS): Time from randomization to death. Subjects alive or lost to follow-up at the end of study (EOS) are censored.

The comparison of OS between the two treatment groups will be performed with a stratified logrank test at the two-sided alpha=0.05 level of significance.

In order to estimate the hazard ratio, a Cox proportional hazards regression model will be fitted with treatment group and the randomization stratification variables as factors [Geographic region (Asia vs. North America/Europe), Disease measurability (measurable vs. nonmeasurable), Prior ramucirumab treatment (Yes vs. No), and Treatment therapy line (3rd vs. ≥4th)].

Kaplan-Meier estimates will be calculated for each treatment group to construct the survival curve. The median overall survival and its 95% CI will also be presented.

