7.5.3 Key Secondary Efficacy Analysis

The key secondary efficacy endpoints (PFS, ORR) will be analyzed using ITT, FAS and PPS. The key secondary efficacy analyses will be conducted using the ITT set.

- Progression Free Survival (PFS): Time from randomization to either documented radiological progression (determined by the central imaging analysis facility) or death from any cause. Subjects alive and free of progression are censored at the last tumor assessment date when alive and free of progression were known.
- Objective Response Rate (ORR): Percentage of subjects with a Best Overall Response (determined by the central imaging analysis facility) of Complete Response (CR) or Partial Response (PR).

PFS will be analyzed using the same statistical methods that are used in the primary efficacy analysis of OS.

ORR will be analyzed using the Cochran-Mantel-Haenszel test stratified by the randomization stratification factors Geographic region (Asia vs. North America/Europe), Prior ramucirumab treatment (Yes vs. No), and Treatment therapy line (3rd vs. ≥ 4th). For the ORR, the frequency and percentage (with 95% CI) of subjects will also be provided.

Data will be summarized in the following tables and figures.

-Table. Progression Free Survival [Independent Central Review] – ITT

-Table. Progression Free Survival [Independent Central Review] – FAS

-Table. Progression Free Survival [Independent Central Review] – PPS

-Figure. Kaplan Meier Plot for Progression Free Survival [Independent Central Review] - ITT

-Figure. Kaplan Meier Plot for Progression Free Survival [Independent Central Review] - FAS

-Figure. Kaplan Meier Plot for Progression Free Survival [Independent Central Review] – PPS

-Table. Objective Response Rate [Independent Central Review] – ITT

-Table. Objective Response Rate [Independent Central Review] – FAS

-Table. Objective Response Rate [Independent Central Review] – PPS

-Table. Progression Free Survival - [Investigator Review] – ITT

-Table. Progression Free Survival - [Investigator Review] – FAS

-Table. Progression Free Survival - [Investigator Review] – PPS

-Table. Objective Response Rate - [Investigator Review] – ITT

-Table. Objective Response Rate - [Investigator Review] – FAS

-Table. Objective Response Rate - [Investigator Review] – PPS

- List. Time to Event Parameters by Subjects – ITT Set

- List. Objective Response by Subject – ITT Set

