12.2 Interim Analysis and Stopping Rules

The interim analysis for futility will be conducted with collected clinical data when approximately 163 (approximately 50% of the required 325 events) events are observed. The independent contract research organization for the interim analysis (AXIO Research, LLC) will conduct all the interim analysis for the study. All planned study procedures such as subject enrollment, treatment and follow-up visit should be performed regardless of the interim analysis. If it is necessary to change the timing of the interim analysis, in consultations with sponsor, the IDMC can change interim analysis time and its corresponding statistical criteria for early termination.

The interim analysis for futility will assess the primary (OS) and key secondary (PFS, ORR) efficacy endpoints using the statistical methods planned for the final analysis but only for ITT population. The interim analysis for futility and two safety reviews will assess adverse events and safety endpoints. The IDMC will review the results of the interim analysis and recommend to the sponsor whether or not to terminate the trial for futility. Final decision regarding study termination will be made by the sponsor.

The IDMC and independent statisticians involved in the interim analysis should keep the interim analysis result completely confidential. The results of the interim analysis should be kept unknown to all staff involved in the conduct of the trial. If early termination is decided, the IDMC delivers the interim analysis report to the sponsor after the official unblinding procedure.

Early termination will be considered if the interim analysis is futile, that is when the calculated conditional power based on primary efficacy endpoint, overall survival (OS), is less than 0.2. The main/official futility analysis will assume future data is distributed as the current data to calculate conditional power (Pepe-Anderson-Betensky test). For additional sensitivity check, conditional power will be calculated assuming future data are distributed according to the alternative hypothesis, specifically hypothesized effect of HR=0.72 (Lan-Simon-Halperin test).

Early stopping for futility interim analysis does not inflate the Type-I error, thus Type I-error adjustment is not needed.

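### The OS p-value and the OS hazard ratio with its 95% CI come from different models, so a borderline result can be reported with an interval that contradicts the test

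*SAP*

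**What the plan says.** **Test.** SAP 7.5.2: "The comparison of OS between the two treatment groups will be performed with a logrank test stratified on the randomization stratification variables". The factors named are region, prior ramucirumab and therapy line, at two-sided 0.05. Measurability is left out; SAP 13 explains that several strata of non-measurable subjects are very small. SAP 7.5.1 makes this test the first gate of the fixed sequence: "Test OS with two-sided 5% level".

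**Estimate.** The next paragraph of SAP 7.5.2 reads: "In order to estimate the hazard ratio, a Cox proportional hazards regression model will be fitted with treatment group as a factor". Four randomization factors, now including measurability, enter "as covariates. The hazard ratio and its 95% confidence interval will be presented". No strata are named for this model.

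**Protocol.** Section 8.3.4 already has this structure: "a Cox proportional hazards regression model will be fitted with treatment group and the randomization stratification variables as factors".

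**PFS.** SAP 7.5.3: "PFS will be analyzed using the same statistical methods that are used in the primary efficacy analysis of OS".

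The visible text specifies no stratified Cox model for OS in the ITT set, FAS or PPS. It does not say what is reported if the CI and the p-value disagree. SAP 13 records the change to the log-rank strata and does not mention the Cox model. The code in SAP 14.5 and 14.6 is redacted and the mock-up tables are not shown, so this reading rests on the wording.

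**The concern.** A stratified log-rank test is the score test of a Cox model with the same strata and treatment as the only covariate. The Wald interval from that Cox model therefore follows the test almost exactly. A Cox model with the factors as covariates assumes one common baseline hazard and additive effects on the log-hazard. It is a different analysis, and its interval can fall on the other side of 1.

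A reader sees the HR, CI and p-value together. Near p = 0.05 two conflicts are possible:
- a CI that crosses 1 beside p < 0.05;
- a CI that excludes 1 beside p ≥ 0.05.

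In the second, a failed primary test is printed next to an interval that reads as success. With no rule fixed beforehand, which result to stress would be chosen after seeing the data.

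**Working it through.** **1. The plan's own figure.** SAP 12.2 gives the design effect ("specifically hypothesized effect of HR=0.72"). SAP 13 gives 325 events for about 80% power, and allocation is 2:1. Schoenfeld's formula gives

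events = (1.960 + 0.842)² / [(2/3)(1/3)(ln 0.72)²] = 7.85 / (0.2222 × 0.1079) ≈ 328.

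With 325 events, √(325 × 2/9) = 8.498. The expected z is 0.3285 × 8.498 = 2.79, and power is Φ(2.79 − 1.96) = 0.797. The stated figures are reproduced within rounding.

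**2. The boundary.** The standard error of the log-HR is about 1/8.498 = 0.118, so the test is significant at an observed HR below about exp(−1.960/8.498) = 0.794.

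**3. How often a result is borderline.** p between 0.03 and 0.08 corresponds to |z| between 1.75 and 2.17.
- At HR 0.72: Φ(2.17 − 2.79) − Φ(1.75 − 2.79) ≈ 0.12.
- At HR 0.794: about 0.17.
- Under the null: 0.05.

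**4. Main simulation.** 4,000 trials per setting, N = 459, 2:1 in blocks of 3 within the 16 randomization strata, analysed at death 325.
- From the documents: uniform accrual over 21 months, and a placebo survival of 4.7 months from the earlier phase III study in Protocol 1.2 (labelled a mean there, used here as a median).
- Assumed: 25% North America/Europe, 10% non-measurable, 35% prior ramucirumab, 38% fourth line or later.
- Four settings, in table order: no prognostic effect; log-HR 0.2 per factor; log-HR 0.3–0.4; baseline hazards not proportional by region (Weibull shape 1.0 v 1.6).

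Percentage of trials in which the 95% CI contradicts the three-factor stratified log-rank verdict:

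| True HR | SAP model, 4 covariates | 3 covariates, no measurability |
|---|---|---|
| 0.72 | 4.3, 4.9, 5.3, 5.2 | 4.5, 4.6, 4.9, 5.0 |
| 0.794 | 4.9, 5.9, 7.0, 8.1 | 5.0, 5.5, 6.3, 7.7 |
| 1.0 | 1.9, 1.9, 1.9, 2.3 | 1.8, 1.7, 1.8, 2.3 |

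A Cox model stratified on the three log-rank factors contradicts the test in 0.05–0.25% across all 12 settings. The Monte Carlo standard error at 5% is √(0.05 × 0.95/4000) = 0.3 percentage points.

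- **Borderline trials** (p 0.03–0.08): 25–36% conflict with the SAP model, against 0.6–2.2% with the stratified Cox model.
- **Direction at HR 0.72:** the CI excludes 1 beside p ≥ 0.05 in 2.9–3.6% of trials, and crosses 1 beside p < 0.05 in 1.3–2.3%.
- **Size of the shift:** the two log-HR estimates differ with SD 0.022–0.030, so the reported HR moves about 2–3%. Against a standard error of 0.118, that is about 0.19–0.25 on the z scale, which is enough to cross 1.96 only near the boundary.

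**5. Cause.** Removing measurability from the covariate model hardly changes the rates (right-hand column). The driver is covariates versus strata, not the fourth factor. A covariate is not a stratum, so keeping measurability in the Cox model does not contradict the small-strata reason in SAP 13.

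**6. Other assumptions.** A second simulation used 1,500 trials per setting, prevalences of 35% (region), 40% (ramucirumab), 35% (line) and 10% (non-measurable), and weak to strong prognostic effects (log-HR about 0.1–0.6). The CI contradicted the test in 3.7–6.5% of trials at HR 0.72, 6.4–9.3% at HR 0.805, and 26–40% when p was 0.03–0.07. The matched stratified Cox model did so in 0.0–0.2% overall.

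**7. PFS.** The earlier phase III study reports: "mPFS also showed the same result (2.6 months versus 1.8 months; HR= 0.444". With a placebo median of 1.8 months, 325 events (assumed) and HR 0.444, there were no conflicts in 16,000 trials. At an assumed PFS HR of 0.70 the rate is 4.7–4.9%.

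**The case against.** The plan is unambiguous about the decision: the log-rank test compares the arms, the Cox model estimates, and a non-significant OS test makes everything after it exploratory. A covariate-adjusted HR beside a stratified test is a legitimate choice. It has been prespecified since Protocol 8.3.4, and it keeps measurability, which a stratified model cannot easily do with such small strata. The overall conflict rate is about 5% at the design effect; the 25–36% applies only to the roughly 12% of trials with a borderline p. The factor prevalences are assumed, and the redacted code or unseen mock-up tables could contain a stratified estimate.

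Most of this stands, and it limits the weight of the point: there is no error in the decision, and the covariate model is valid. The exact rates depend on the assumptions, as the wider ranges from the second set show, although even with no prognostic effect the rate is 4.3% at HR 0.72. The redaction cannot be resolved from the documents; if the code does stratify, the SAP text still needs correcting to match it. A sentence saying that the log-rank test governs would settle which result counts, but the conflicting interval would still be the headline estimate.

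**Conclusion.** The concern holds as a reporting defect that should be fixed; it does not threaten validity. On the visible wording, the OS test and the only specified OS interval are different analyses. At HR 0.72 they disagree about significance in roughly 4–6% of trials. Near the boundary the rate is about 5–9%, and under the null about 2%. The commoner conflict is an interval that excludes 1 beside a failed test. The direction is the same under every set of assumptions tried; the exact rates rest on assumed prevalences and prognostic effects. For PFS a conflict is unlikely if the effect is as large as in the earlier phase III study.

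**What to change.** Replace the estimation sentence in SAP 7.5.2 with wording such as:

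> The OS hazard ratio and its 95% CI will be estimated from a Cox model with treatment as the only covariate, stratified by geographic region, prior ramucirumab treatment and treatment therapy line, as in the log-rank test. The Cox model with all four randomization factors as covariates will be reported as a sensitivity analysis.

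Use the same model for PFS for consistency, and add a row to SAP 13 before unblinding. State whether the FAS and PPS tables, the investigator-assessed PFS tables and the subgroup analyses with their forest plot follow the same model, since they draw on the same method.

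**Cost.** The core change is one sentence, one STRATA statement and one SAP 13 row; the tables above need the same decision. The headline estimate no longer adjusts for measurability. Across the OS settings of the main simulation, the log-HR standard error rises by 1.5–2.3%. At HR 0.72 the CI excludes 1 in 78.5–79.7% of trials instead of 79.5–81.7%. The deciding test, its power, the sample size and the event count do not change.
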